## Louis Stokes Cleveland Department of Veterans Affairs Medical Center Research Plan

Please contact the IRB office if you have any questions at [contact] [name].

Request for Expedited IRB Review Form attached

**Human Subject Research:** Human subject research means research involving interaction or intervention with living human beings or access to identifiable private information of living human beings.

**Research Plan:** The information requested in the Research Plan is designed to provide the IRB with the necessary information such that it can make the federally required determinations codified at 38 CFR Part 16, 21 CFR Parts 50, 54, & 56, and 45 CFR Part 46

The **Research Plan** is to be written so that the non-scientist/non-medical members of the IRB can understand the research proposed. Define all abbreviations and terms that are not part of common language.

**Version Date:** This should be updated subsequently with every modification to any part of the Research Plan. Any modification to this document, no matter how minor, must be reviewed and approved by the IRB prior to implementation. The Research Plan will be stamped with the date of IRB approval

## Section 2 – Research Sites and Sponsor

5. Please list all Research Sites in addition to Louis Stokes Cleveland DVA Medical Center (LSCDVAMC);

International studies when the PI is the Lead Investigator list the countries:

a. When study procedures including analysis of identifiable samples or data involving LSCDVAMC enrolled subjects will be conducted at any site other than the LSCDVAMC please provide the following:

Name and contact information for the site:

Describe the plan for communicating protocol amendments, reports of serious adverse events, reports of unanticipated problems involving risks to subjects or others, interim reports, and DSMB reports to external sites.

\* When the LSCDVAMC is considered the coordinating center and the PI the lead investigator on cooperative research or a multi-center trial contact AO/Research [[contact]](mailto:[contact]).

6. Sponsor or other Support (*list industry sponsor, government support, etc.*):

VA SPiRE Grant from the Rehabilitation Research and Development Service of the Veterans Affairs.

## Section 3 – Research Design and Procedures

7. Definitions- Provide a list of all abbreviations and specialized terms to be used in this document and their definitions:

| Abbreviations / Specialized Terms
(Use the Enter key in this column to insert additional abbreviations and their definitions) | Definition                                |
|--|---|
| BF   | biceps femoris                            |
| BP   | blood pressure                            |
| CNS  | central nervous system                    |
| CV   | cyclical vibration                        |
| EDSS   | Kurtzke Expanded Disability Status Scale  |
| EMG  | electromyogram                            |
| HR   | heart rate                                |
| LSCDVAMC   | Louis Stokes Cleveland DVA Medical Center |
| MS   | multiple sclerosis                        |
| RF   | rectus femoris                            |

| Abbreviations / Specialized Terms
(Use the Enter key in this column to insert additional abbreviations and their definitions) | Definition                         |
|---|------------------------------------|
| TA  | tibialis anterior                  |
| TFL   | tensor fasciae latae               |
| VGB   | Volitional gait at baseline        |
| VGP   | Volitional gait post-training      |
| VHA   | Veterans Health Administration     |
| VSCU  | vibration stimulation control unit |

8. Provide a BRIEF SUMMARY of the background for this research. DO NOT CUT and PASTE paragraphs that do NOT summarize the background.

- *Include a critical evaluation of existing knowledge, and specifically identify the information gaps that your protocol is intended to fill.*
- *Refer to appropriate citations in the scientific literature and include your references at the end of this section.*
- *Include the rationale for conducting the research at the VA.*

Multiple sclerosis (MS) is a chronic and progressive inflammatory demyelinating disease of the central nervous system (CNS) with an underlying neurodegenerative component that impairs walking ability in 50% to 75% of approximately 400,000 affected people in the U.S [1, 2, 3]]. Patients with MS generally develop weakness in their lower extremities of hip and knee flexors and ankle dorsiflexors requiring high effort to swing their leg forward for walking through hiking or circumduction. Dorsiflexion can be easily corrected with the simple ankle foot orthosis or surface electrical stimulation of the common peroneal nerve. However, there is currently no practical and clinically available solution to providing strong, repeatable and effectively coordinated hip and knee flexion for safer, more stable and natural gait required for overcoming uneven terrain, slopes, and stairs encountered in activities of daily living.

This work is directly applicable to the health, wellbeing and functional independence of the disabled veteran from CNS disorders. More than 16,000 veterans with MS receive care in the VHS and over 6,000 of those have service connection for MS [5]. However, these numbers do not fully reflect the entire scope of the problem since they do not include the thousands of spouses, children or other family members who live with and care for veterans with MS and have had to alter their own lifestyles as a result of the motor dysfunction of their loved ones. Treatment of MS includes complex and expensive pharmacologic agents as well as multidisciplinary medical and rehabilitation services and assistive technology [5]. Gait impairment is associated with increased health complications, injury from falls, social isolation from immobility and decreased quality of life measures [4]. Therefore, preventing further disability by improving walking in veterans with MS is an important potential intervention.

With the help of cyclical vibration (CV), many veterans with MS may experience improved walking since some of their motor, sensory and proprioceptive functions are preserved and can be amplified.

The primary goal of this pilot study is to explore the feasibility of cyclic vibration of the lower extremity muscles to improve walking in veterans with gait deficits from MS. Vibration is perhaps the most potent mechanical stimulus for activating muscle spindle primary afferents (Ia) [1]. This facilitates excitability of corticospinal projections to the target muscles while the  $\alpha$ -efferents to antagonists are inhibited. Since it has been shown that cyclical vibration promotes normal patterns of motor activity by modulating the excitability of motoneurons projecting to target muscles, *it is hypothesized that facilitatory effects of cyclical muscle vibration of hip, knee and ankle muscles improves 1) walking speed and foot-to-floor clearance through increased hip and knee pre-swing flexion and improved hip-knee coordination, 2) induces carryover effects that maintain improved walking after application and 3) produces no untoward sensations or adverse physiological responses.* In previous studies vibration to the dorsiflexor muscle tibialis anterior [2] alone and in combination with the hip abductor gluteus medius [3] resulted in improved walking speed in individuals with hemiplegia. Similarly, cyclical vibration increased muscle excitation with phase dependent changes in the timing of muscle activation during gait [4] and multi-channel complex vibration patterns exhibited gait-like leg movements that present a potential for rehabilitation [5].

Therefore, this pilot study is designed to explore the efficacy and safety of cyclical vibration at correcting the typical gait deficits that involve strength and coordination of multiple joints (hip, knee and ankle) in pre- and early swing and determine whether the new intervention warrants a full comprehensive study to quantify its facilitatory effects on gait improvement in veterans with MS.

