**11. Provide a BRIEF DESCRIPTION of how the estimated number of study subjects needed for this research was determined**

- *If this is a quantitative study provide the method of determining sample size estimates.*
- *If multiple studies are planned provide a power analysis or justification for each one.*

A statistical power of 90% was used to determine the number of trials with VICON motion analysis system required for the testing and comparison of temporal and spatial gait parameters. The results indicated a requirement of 30 strides of data or roughly 6 trials (approximately 5 strides per trial) for each condition (volitional or CV). Because this is a two year feasibility study to determine the effect size a small sample of 6 subjects were chosen for intervention with six controls to obtain preliminary data for calculating statistical power for the number of subjects required in a larger study to determine the effect of vibration on improving gait in MS.

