**Recruitment and baseline evaluation**

Potential subjects will be identified via chart review or through referral and asked if they would be willing to participate in the study. If agreeing, they would undergo the consent process. Twelve subjects with gait disorders from MS will be recruited for participation in this study, with six subjects assigned to undergo CV gait training and six to control group for gait training without vibration. Subjects will be randomly assigned to either treatment or control group and matched by functional walking category based on speed for data analysis†. After signing the consent form agreeing to participate in the study and meeting inclusion/exclusion criteria, subjects will undergo baseline evaluation. This will include walking speed and distance and using VICON system for temporal and spatial parameters, kinematics and kinetics of gait and EMG activity during volitional gait at their preferred walking speed.

Retro-reflective markers will be placed on the bony landmarks and surface EMG electrodes over target muscles while the subject walks along the 10m walkway instrumented with force platforms. Standard analysis software provided with VICON system will be used to track markers in 3D and calculate all gait parameters so they can be correlated with muscle activity. The baseline evaluation will be done with and without vibration on treatment group and without vibration on control group. Data will be collected during 6 walking trials of at least 5 steps per trial (approximately 30 steps) within the visual field of the VICON motion analysis system under each condition. Sufficient resting time will be provided between trials to complete the assessment. Subjects will be encouraged to use their walking aid while a trained physical therapist provides standby guard during walking for their safety.

[figure not shown]

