### Gait training

Each group will undergo twelve 2 hour sessions of standard gait training (up to 3x/week based on availability). Both groups will receive the same gait training while the treatment group will receive gait training with CV and control group without it.

Up to four vibrators per leg powered by the vibration stimulation control unit (VSCU) will be strapped or taped over ankle dorsiflexor tibialis anterior (TA), knee extensor and hip flexor rectus femoris (RF), knee flexor short head of biceps femoris (BF) and hip flexor and abductor the lateral portion of tensor fasciae latae muscles (TFL) as shown in figure. The cylindrical vibrators will be used to increase vibration intensity as needed. The CV paradigm resembling normal activity of muscles timed to gait events, as detected by accelerometers taped to the shoes and force sensing resistors placed in the insoles, will be imposed during walking. An average frequency of vibration will be set at 80Hz and as high as 150Hz. Physical therapist will conduct all gait training and encourage maximal voluntary effort during training while providing standby assist and spotting the subjects to ensure safety. During walking, heart rate (HR) will be monitored with the chest strap monitor and receiver watch and recorded before and after each walk. Blood pressure (BP) will be measured before and after each session of CV training and evaluation. In addition, subjects will be asked during each session if they experience any untoward sensation. BP and HR during gait training with vibration will be monitored and compared to baseline values. An increase in BP and HR of >20% and experiencing untoward sensation will be considered significant to reject Hypothesis that CV produces no physiological changes.

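### Hypothesis 3 claims that vibration produces no adverse effects, but an event-free result in about six vibrated subjects cannot support that, and neither document gives a rate, bound or interval

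*Protocol*

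**What the plan says.** Item 9 of the protocol states three hypotheses. The third is that vibration "produces no untoward sensations or adverse physiological responses". The same item says that "this pilot study is designed to explore the efficacy and safety of cyclical vibration" and that the pilot should help decide whether a full study is warranted.

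The only decision rule for Hypothesis 3 is in item 13, under Gait training: "An increase in BP and HR of >20% and experiencing untoward sensation will be considered significant to reject Hypothesis that CV produces no physiological changes". Nothing is said about how to read the result if the rule is not met.

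On numbers, item 13 plans for twelve subjects, "with six subjects assigned to undergo CV gait training and six to control group for gait training without vibration". It also states: "The baseline evaluation will be done with and without vibration on treatment group and without vibration on control group". Item 11 explains that "a small sample of 6 subjects were chosen for intervention with six controls to obtain preliminary data for calculating statistical power" for a larger study.

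Item 10 assigns the repeated-measures ANOVA and the Tukey comparisons to Hypotheses 1 and 2 only. The SAP offers means, standard deviations and a two-way ANOVA. It contains no safety analysis.

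**The concern.** Hypothesis 3 is a universal negative, and the only test attached to it can reject it but cannot confirm it. The one favourable outcome open to it is that the rejection rule is not met. In about six people, that outcome is compatible with a substantial event rate. The documents supply nothing else to report: no estimate of how often a vibrated subject has an event, and no statement of how high that rate could still be. Whoever plans the next study needs that second figure.

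Two features of the plan make an event-free result easier to obtain. The rule joins blood pressure, heart rate and sensation with the word *and*, so on a literal reading one kind of event alone might not trigger it. Item 30 also admits only people who tolerate muscle vibration without an untoward sensation, so reactions at screening are removed before counting starts.

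**Working it through.** **Inputs**
- Subjects training with vibration: n = 6 (items 11 and 13). Controls have no vibration at baseline or in training, so the denominator for vibration events is 6, not 12.
- Event: scored once per subject as yes or no, with subjects independent (assumption).
- Confidence level: 95% (assumption; item 10 uses 95% for Hypotheses 1 and 2 only).
- True event rates of 10%, 20% and one third: illustrative assumptions, since the documents give none.

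**Step 1: the plan's own figures.** 6 + 6 = 12 subjects, and 6 trials × 5 strides = 30 strides; both agree. The 90% power in item 11 and the SAP concerns the number of walking trials. No effect size or SD is given, so it cannot be reproduced, and it does not concern safety. There is no safety figure to reproduce.

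**Step 2: upper limit with no events.** Solving (1 − p)^n = a gives p = 1 − a^(1/n). For n = 6:
- one-sided 95%: 1 − 0.05^(1/6) = 0.393
- two-sided 95% (Clopper-Pearson): 1 − 0.025^(1/6) = 0.459
- Wilson 95%: 1.96² / (6 + 1.96²) = 3.84 / 9.84 = 0.390
- one-sided 90%: 1 − 0.10^(1/6) = 0.319
- Jeffreys, 97.5% point: 0.330

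The level must therefore be stated. The exact and Wilson 95% limits exceed one third, but the last two fall just below it.

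**Step 3: chance of seeing no event in six subjects,** (1 − p)^6:
- p = 10%: 0.9^6 = 0.531
- p = 20%: 0.8^6 = 0.262
- p = one third: (2/3)^6 = 0.088

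**Step 4: if the number exposed is not six.** Item 14 allocates by coin toss. With 12 subjects and no restriction, the chance of exactly six per arm is 924/4096 = 22.6%. The formula in Step 2 gives:

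| Subjects exposed, no events | One-sided 95% | Two-sided 95% |
|---|---|---|
| 4 | 52.7% | 60.2% |
| 5 | 45.1% | 52.2% |
| 6 | 39.3% | 45.9% |
| 7 | 34.8% | 41.0% |
| 8 | 31.2% | 36.9% |

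**Step 5: sessions instead of subjects.** Six subjects × 12 sessions = 72 subject-sessions, and 1 − 0.05^(1/72) = 0.041. That limit needs independent sessions, but these are repeated within six people. It does not answer how many patients would be affected.

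**The case against.** The strongest reply is that the plan never says it will accept Hypothesis 3. A reader might infer that an event-free result will be declared proof of safety and used as a criterion for going on to the full study. The documents do not support that: item 13 states only when the hypothesis is rejected, and item 9 ties the decision on a full study to no particular safety result. A reader might also infer that harm in more than a third of patients could go unseen. That is too strong as well. The defined events are rises in blood pressure and heart rate and untoward sensations, in people pre-screened for tolerance, and the figure depends on the confidence level. Both limits on the point stand.

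The study is also an openly declared pilot. Items 9 and 11 and the SAP acknowledge the preliminary purpose, and the SAP concedes that the small sample limits generalizability. No pilot of this size could bound a rate tightly. This is fair, but the caveats are general and none says what an event-free result can show about safety.

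Detection of problems does not depend on Hypothesis 3 alone. Sensations are asked about at each session (item 13), adverse events are gathered and reported (item 53), and grounds for removal are listed (item 65). These procedures find events; they do not supply a rate or an interval.

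The event itself is loosely defined. Item 9 speaks of adverse responses and item 13 of any physiological change, and the baseline values for comparison are not specified. Depending on how these are read, effort from walking might cross the threshold, and the rule could then reject without separating vibration from exercise. This is a further reason to report counts beside the control arm.

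Finally, six is not a secure denominator. Allocation is by coin toss, item 20 screens up to 48 people to have 12 complete, and item 65 allows removals. The interval should use the actual number exposed.

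**Conclusion.** The point holds as a mismatch between an absolute hypothesis and what about six exposed subjects can show. With 0 of 6 affected, per-subject rates of the defined events up to 39% (one-sided 95%) or 46% (two-sided 95%) remain compatible with the data. If the true rate were 10%, no event would be seen in 53% of such trials, more often than not.

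These figures assume independent subjects, one yes-or-no score per subject and six exposed. They describe people already screened to tolerate vibration. The fault lies in the wording of the hypothesis and the missing interval; the size of the pilot is not at fault.

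**What to change.** Make Hypothesis 3 descriptive in item 9 and in the Gait training part of item 13. Reconcile the two wordings, adverse responses in one and any physiological change in the other. State whether the components of the rule count jointly or separately, and what baseline they are compared with.

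Add to the SAP:

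*The number of subjects with each pre-specified safety event among all n subjects exposed to vibration, including those removed or withdrawn, will be reported with its exact two-sided 95% confidence interval, beside the control-arm number where collected. Zero events will be reported as an upper bound (for example, 46% if n = 6) and not as showing that vibration produces none.*

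The cost is some rewording and one exact binomial interval per event. The safety statement becomes less favourable. No more patients are needed.

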#### 10. Describe the means of analyzing the data and evaluating the results.

- *State the anticipated methods to be used for analysis and interpretation of the data.*
- *The methods must compliment the design of the study and the nature of the data which is being collected.*

Primary outcome measures for testing hypotheses will be walking speed measured during 10m walk trials and foot-to-floor clearance as measured by vertical displacement of marker placed over the first metatarsal using our 16-camera VICON motion analysis system. Force sensing resistors (FSRs) will be used to detect any toe dragging as a result of insufficient foot clearance. Secondary measures will be peak hip, knee and ankle flexion during swing, hip-knee coordination changes, knee flexion during stance and in pre-swing, step length symmetry and 6min walking distance.

The within subject experimental design will be used because it requires fewer subjects with more statistical power while reducing the potential for systemic error or selection bias to test the effect of CV on walking. While practice and carryover effects are major disadvantages of this study design, proper precautions including rest periods between tests and randomization of testing order for treatment group will be instituted to minimize them†. In addition to comparison between treatment and control groups, subjects receiving CV can also serve as their own controls by first comparing volitional gait at baseline (VGB) with any gait correction with the CV approximating desired normal muscle activity (CVN). Next the volitional gait *post*- 12 sessions of training with vibration (VGP) will be compared to volitional gait at baseline (VGB). Thus, any improvements at baseline with CVN compared to volitional gait (VGB) can be attributed to short term effects of vibration. Improvements in volitional gait *post* training with vibration (VGP) compared to baseline gait (VGB) will be attributed to long term effects of vibration. The control group subjects will be evaluated at baseline (VGB) and after gait training (VGP) and compared to the intervention group to identify trends and further explore the potential effects of CV. While this study design has limited generalizability due to the inhomogeneity of the selected population, it can be quite useful for developing and refining CV intervention.

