A one-way repeated measures ANOVA will be used to test for significant difference between means to test Hypotheses 1 and 2. The Tukey honestly significant difference multiple comparison test will be used between each pair of mean walking speeds, foot-to-floor clearance and maximum joint angles to determine 95% ( $p < 0.05$ ) confidence intervals for

statistically significant differences between conditions (CVN-VGB, CVN-VGP, VGP-VGB) and between groups to identify trends across all subjects.

† Greenwald AG. With-in subject design: to use or not to use? *Psychological Bulletin*, 83(2):314-320, 1976.

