Statistical Analysis Plan

Study Title: Cyclical muscle vibration in multiple sclerosis to improve walking

Last update: 01/29/2020

The within subject experimental design was used for this feasibility study because it requires fewer subjects with more statistical power while reducing the potential for systemic error or selection bias to test the effect of training with vibration on walking. While practice and carryover effects are major disadvantages of this study design, proper precautions including rest periods between tests and randomization of testing order for walking with or without vibration was instituted to minimize them at baseline and post-treatment¹. In this study design, any improvements at baseline with vibration compared to volitional gait can be attributed to short term effects of vibration. Improvements in volitional gait *post* training with vibration compared to volitional baseline gait can be attributed to long term effects of vibration. While this feasibility study design has limited generalizability due to the small number of subjects and inhomogeneity of the selected population, it can be quite useful for developing and refining future vibration intervention studies.

Means and standard deviations were calculated for all outcome measures for each subject. Differences in means were determined via a two-way analysis of variance ($p < 0.05$). A statistical power of 90% was used to determine the number of trials with VICON motion analysis system required for the testing and comparison of gait parameters. The results indicated a requirement of 30 strides of data or roughly 6 trials (approximately 5 strides per trial) for each condition (volitional or with vibration).

¹ Greenwald AG. With-in subject design: to use or not to use? *Psychological Bulletin*, 83(2):314-320, 1976.

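### The plan credits the treated arm's gain after training to vibration, although both arms get the same gait training; only the arm difference in change separates the two, and no contrast is tied to the full-study decision

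*Protocol*

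**What the plan says.** **Decision.** Protocol item 9 opens with "The primary goal of this pilot study is to explore the feasibility of cyclic vibration of the lower extremity muscles" and ends by saying that the study will "determine whether the new intervention warrants a full comprehensive study to quantify its facilitatory effects on gait improvement in veterans with MS". Neither statement carries a criterion.

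**Outcomes.** Item 10: "Primary outcome measures for testing hypotheses will be walking speed measured during 10m walk trials and foot-to-floor clearance". The two are not ranked.

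**Contrasts.** Item 10 defines volitional gait at baseline (VGB), gait with vibration on at baseline (CVN) and volitional gait after training (VGP). It reads CVN-VGB as the short-term effect of vibration. For VGP it says that improvement "compared to baseline gait (VGB) will be attributed to long term effects of vibration". The SAP keeps both readings, with the softer verb that such gains can be attributed to vibration.

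**Tests.** Item 10: "A one-way repeated measures ANOVA will be used to test for significant difference between means to test Hypotheses 1 and 2", followed by Tukey comparisons for "statistically significant differences between conditions (CVN-VGB, CVN-VGP, VGP-VGB) and between groups to identify trends across all subjects". The SAP has instead "Differences in means were determined via a two-way analysis of variance", and names neither the factors nor the error term.

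**Controls.** Item 10 measures controls at VGB and VGP and compares them with the intervention group to look for trends. The SAP does not mention a control group.

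**Training.** Item 13 gives both arms the same twelve sessions of two hours, with vibration added in one arm only.

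**The concern.** The treated arm's VGP-VGB change adds together whatever 24 hours of supervised gait training does (12 x 2 h) and whatever vibration adds to it. The plan assigns the whole sum to vibration. The control arm was included and randomised, and could supply the training part for subtraction, but its comparison is reduced to a search for trends and then drops out of the SAP.

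This matters because item 9 makes the pilot the basis for deciding on a full study and no other contrast is named as deciding. If gait training works by itself, following the plan's attribution rule leads to the conclusion that vibration has a lasting effect when it may have none. Item 11 also says that the pilot is to supply the effect size for a larger study, without saying from which contrast. Taken from the treated arm alone, that effect size would include training.

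**Working it through.** **The plan's own figure.** Item 11 and the SAP give 6 trials x about 5 strides = 30 strides per condition at 90% power. The product agrees. The power cannot be reproduced, because no effect size, SD or test is given. It concerns strides, not subjects; the 6 + 6 subjects carry no power calculation.

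**What each contrast estimates.** Let T be the effect of training, including practice and time, and V the addition from vibration over the training period.
- Treated arm, VGP-VGB: T + V
- Control arm, VGP-VGB: T
- Arm difference in change: (T + V) - T = V
- Treated arm, CVN-VGB: immediate effect with vibration on, with no training in between

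The treated-arm change equals V only if T = 0, and the documents give no reason to assume that.

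**How often this would mislead.** The documents give no training effect, SD or correlation, so these inputs are assumed:
- 6 treated subjects with VGB, CVN and VGP; 6 controls with VGB and VGP; V = 0, and no immediate vibration effect
- independent unit-variance errors, so the SD of change is sqrt(2)
- two primary outcomes, correlation 0.5
- T the same in both arms: 0, 0.5 or 0.8 SD of change
- within the treated arm: Tukey, significant if the difference in means exceeds q(0.05; 3, 10) x sqrt(MSE/6)
- between arms: two-sample t-test on change, 10 df, critical value 2.228
- 40,000 simulated trials per setting

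Columns A to C count only significant results that favour vibration. A is at least one of CVN-VGB, VGP-VGB or the arm difference, on either outcome. B is the same without within-arm VGP-VGB. C is within-arm VGP-VGB on one outcome. D is the arm difference on one outcome, two-sided.

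| T (SD of change) | A | B | C | D |
|---|---|---|---|---|
| 0 | 7% | 6% | 1% | 5% |
| 0.5 | 20% | 6% | 11% | 5% |
| 0.8 | 42% | 6% | 27% | 5% |

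For correlations from 0.8 down to 0, column A runs 6 to 8%, 18 to 22% and 37 to 48%. The rise from B to A comes wholly from within-arm VGP-VGB.

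**Precision of the arm difference at 6 v 6.** The 95% CI half-width is 2.228 x sqrt(1/6 + 1/6) = 2.228 x 0.577 = 1.29 SD of change. With noncentrality d x sqrt(3) on 10 df, 80% power needs d = 1.80 and 90% needs d = 2.08. Power is 12% at d = 0.5, 24% at 0.8 and 35% at 1.0.

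**The case against.** **It is a feasibility pilot.** Item 10 treats group comparisons as exploratory, and item 11 says that the sample was chosen to obtain preliminary data. That is fair, and it argues against demanding a powered test. It does not rescue the attribution rule: item 9 assigns the pilot a decision, and crediting T + V to vibration is wrong at any sample size.

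**The contrasts already have roles.** Item 10 ties CVN-VGB to short-term and VGP-VGB to long-term effects, and it does plan a comparison with controls. This stands in part. CVN-VGB has a sensible role and adds little false-positive risk here. The fault lies in the role given to within-arm VGP-VGB.

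**Subjects are stable.** Item 30 requires a gait deficit present for at least three months without improvement. That limits spontaneous recovery, but not a response to 24 hours of training.

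**A stronger reading.** A reader might infer that any one significant pair would trigger a full study, and so count every significant test. In the same simulation that gives 16%, 34% and 60%. The documents do not support this. No such rule is written, and the count includes significant worsening and CVN-VGP differences, neither of which favours going ahead.

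**Timing and criterion.** The SAP, last updated 01/29/2020, is written in the past tense, so a contrast named now may be post hoc. It would also still lack a numerical threshold for proceeding, and the documents contain no figure from which to derive one. Both points stand as limits on the remedy.

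**Conclusion.** The point holds. No contrast is tied to the decision on a full study, and the one rule that the plan does state for long-term effects uses a contrast that cannot separate vibration from the training given to both arms.

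The size depends on how well training works alone, which the documents do not say. With no vibration effect, the chance of a result favouring vibration is 7% if training does nothing, and 20% or 42% at assumed training effects of 0.5 or 0.8 SD of change. It stays near 6% once within-arm VGP-VGB is set aside. These figures assume subject-level analysis, independent errors and an outcome correlation of 0.5. They describe how often the planned tests would look favourable, not the error rate of a written go/no-go rule, since none exists.

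It would go too far to say that the listed tests conflict with one another, or that false positives are frequent in general. Under these assumptions the problem is confined to one contrast and grows only as training itself works.

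**What to change.** In items 9 and 10 and in the SAP:
- State that the conclusion on long-term (training) effects, and hence on a full training study, rests on the between-arm difference in VGP-VGB change in the primary outcomes, walking speed and foot-to-floor clearance. Analyse it with the subject as the unit and report the estimate with its 95% CI whatever the p-value.
- Delete the sentences attributing within-arm VGP-VGB change to vibration, and label that contrast supportive.
- Keep CVN-VGB for the separate question of the immediate effect with vibration on.
- Restore the control group to the SAP, and name the same arm difference in item 11 as the source of the effect size for a larger training study.
- Say that feasibility and safety remain part of the decision.

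If results have already been seen, date the change and report it as such; the correction to the interpretation is needed either way.

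**Cost.** Wording only: item 13 already provides for the measurements in both arms. The real downside is precision. At 6 v 6 the half-width is about 1.29 SD of change and about 1.8 SD is needed for 80% power, so a useful effect of vibration may well not reach significance. The result should be read as an estimate with wide limits. A gain seen only within the treated arm would no longer support a claim of lasting benefit on its own.
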